#### NOTES:

Stable chronic liver disease should generally be defined by the absence of ascites, encephalopathy, coagulopathy, hypoalbuminaemia, oesophageal or gastric varices,

**CONCURRENT CONDITIONS/MEDICAL HISTORY (INCLUDES LIVER FUNCTION AND QTc INTERVAL)**

or persistent jaundice, or cirrhosis

4. **Hepatitis status:** Diagnosis of chronic hepatitis B, as evidenced by positive Hepatitis B surface antigen (HBsAg) at Visit 1. Chronic stable hepatitis C (e.g., positive hepatitis C antibody test result at screening (Visit 1) or within 3 months prior to first dose of study treatment) are acceptable if subject otherwise meets entry criteria.

5. **Cardiovascular:** Subjects who have severe or clinically significant cardiovascular disease uncontrolled with standard treatment. Including but not limited to:

- a. known ejection fraction of <30% **OR**
- b. severe heart failure meeting New York Heart Association Class IV (see [Appendix 4](#)) classification **OR**
- c. hospitalised in the 12 months prior to Visit 1 for severe heart failure meeting New York Heart Association Class III (see [Appendix 4](#))  
**OR**
- d. angina diagnosed less than 3 months prior to Visit 1 or at Visit 1

6. **Subjects with QTc > 450 msec or QTc > 480 msec in subjects with Bundle Branch Block at screening Visit 1**

NOTES:

- The QTc is the QT interval corrected for heart rate according to Bazett's formula (QTcB), Fridericia's formula (QTcF), and/or another method, machine-read or manually over-read.
- The specific formula that will be used to determine eligibility and discontinuation for an individual subject should be determined prior to initiation of the study. In other words, several different formulae cannot be used to calculate the QTc for an individual subject and then the lowest QTc value used to include or discontinue the subject from the trial.
- For purposes of data analysis, QTcB, QTcF, another QT correction formula, or a composite of available values of QTc will be used as specified in the Reporting and Analysis Plan (RAP).

7. **Other Concurrent Medical Conditions:** Subjects who have known, pre-existing, clinically significant endocrine, autoimmune, metabolic, neurological, renal, gastrointestinal, hepatic, haematological or any other system abnormalities that are uncontrolled with standard treatment.

8. **Eosinophilic Diseases:** Subjects with other conditions that could lead to elevated eosinophils such as Hypereosinophilic Syndromes, including Churg-Strauss Syndrome (Eosinophilic Granulomatosis with Polyangiitis; EGPA), or Eosinophilic Esophagitis.

**CONCURRENT CONDITIONS/MEDICAL HISTORY (INCLUDES LIVER FUNCTION AND QTc INTERVAL)**

Subjects with a known, pre-existing parasitic infestation within 6 months prior to Visit 1 are also to be excluded.

9. **Immunodeficiency:** A known immunodeficiency (e.g., human immunodeficiency virus – HIV), other than that explained by the use of corticosteroids taken as therapy for asthma.

**CONCOMITANT MEDICATIONS**

10. **Other Monoclonal Antibodies:** Subjects who have received any monoclonal antibody (other than omalizumab) to treat inflammatory disease within 5 half-lives of Visit 1.

**RELEVANT HABITS**

11. **Smoking history:** Current smokers or former smokers with a smoking history of  $\geq 10$  pack years (number of pack years = (number of cigarettes per day / 20) x number of years smoked). A former smoker is defined as a subject who quit smoking at least 6 months prior to Screening Visit 1.

12. **Alcohol/Substance Abuse:** A history (or suspected history) of alcohol misuse or substance abuse within 2 years prior to Visit 1.

13. **Adherence:** Subjects who have known evidence of lack of adherence to controller medications and/or ability to follow physician's recommendations.

**CONTRAINDICATIONS**

14. **Hypersensitivity:** Subjects with allergy/intolerance to a monoclonal antibody or biologic.

History of sensitivity to any of the study medications, or components thereof or a history of drug or other allergy that, in the opinion of the investigator or Medical Monitor, contraindicates their participation.

**DIAGNOSTIC ASSESSMENTS AND OTHER CRITERIA**

15. **Investigator opinion:** Omalizumab treatment has provided significant clinical benefit despite experiencing 2 exacerbations in the past 12 months, and potential benefit from a switch to mepolizumab would not outweigh the potential harm after omalizumab withdrawal for the subject.

16. **Previous participation:** Previously participated in any study with mepolizumab and received investigational product (including placebo).

**DIAGNOSTIC ASSESSMENTS AND OTHER CRITERIA**

17. **Investigational Medications:** Subjects who have received treatment with an investigational drug within the past 30 days or five terminal phase half-lives of the drug whichever is longer, prior to Screening (V1) (this also includes investigational formulations of marketed products).

18. **Pregnancy:** Subjects who are pregnant or breastfeeding. Patients should not be enrolled if they plan to become pregnant during the time of study participation.

**5.3. Continuation to Treatment Criteria**

At Visit 2, those subjects who fulfil the inclusion/exclusion criteria and who meet the continuation to treatment criteria will commence the study treatment phase until the target of approximately 120 treated subjects is reached.

In order to receive study treatment subjects must have completed the run-in period and must have fulfilled all inclusion and exclusion criteria described in Section 5.1 and Section 5.2. In addition to the following:

**REQUIRED CRITERIA TO START TREATMENT**

1. **Not optimally controlled:** An ACQ-5 score of  $\geq 1.5$  recorded at Visit 2
2. **No Asthma Exacerbation:** Subjects with an ongoing asthma exacerbation at Baseline (Visit 2) should have their Visit 2 delayed until the investigator considers the subject has returned to their baseline asthma status for at least one week. If the 4-week screening/run-in period has elapsed and subjects have not returned to their baseline asthma status, then they should be considered a run-in failure. An exacerbation is defined as worsening of asthma requiring the use of systemic corticosteroids and/or emergency department visit, or hospitalisation (see Section 7.3.2.4 Clinically Significant Asthma Exacerbation).
3. **Maintenance Asthma Therapy:** No changes in the dose or regimen of ICS and/or additional controller medication (except for treatment of an exacerbation) during the run-in period.
4. **Last dose of omalizumab:** For subjects receiving omalizumab every 4 weeks, their last dose must be 3 to 5 weeks prior to Visit 2. For subjects receiving omalizumab every 2 weeks, their last dose must be between 1 to 3 weeks prior to Visit 2.

**5.4. Pre-Screening/ Screening/Run-in Failures**

A subject will be assigned a subject number at the time the informed consent is signed.

A subject who is assigned a subject number at Visit 0 but does not have any screening Visit 1 procedures will be considered a pre-screen failure.

The following information will be collected in the eCRF for subjects who are pre-screen failures:

- Date of ICF signature
- Demographic information including race, age and gender
- Child bearing status assessment for all female subjects of reproductive potential
- Subject number
- Details of asthma medications within 3 months of the pre-screening Visit 0
- Details of asthma exacerbations during the pre-screening period
- Serious Adverse Event information only for any SAE considered as related to study participation (e.g. protocol mandated procedures, invasive tests or change in existing therapy) or related to a GSK concomitant medication
- Investigator signature page

For the purposes of this study, screening failures and run-in failures will be defined as follows:

- **Screening failures:** those subjects that complete at least one Visit 1 (Screening) procedure but do not enter the run-in period.
- **Run-in failures:** those subjects that enter the run-in period but do not subsequently receive study treatment.

Subjects who are pre-screen, screen and run-in failure will be recorded in the eCRF.

## 5.5. Withdrawal/Stopping Criteria

### 5.5.1. Withdrawal from Study Treatment

Subjects may be withdrawn from study treatment at any time by the Investigator if it is considered to be detrimental for them to continue in the study. Reasons for withdrawal from study treatment can include: an adverse event (including abnormal liver function test or abnormal laboratory results), clinically significant abnormality identified on ECG, lost to follow-up, protocol violation, lack of efficacy, sponsor terminated study, non-compliance, continued in error, pregnancy, or for any other reason.

Subjects who have permanently withdrawn mepolizumab study treatment are not required to withdraw from the study. Every effort should be made to complete all remaining protocol specified visits even if they have discontinued mepolizumab treatment provided there are no safety concerns with doing so.

### 5.5.2. Withdrawal from the Study

A subject may withdraw from study at any time at his/her own request, or may be withdrawn at any time at the discretion of the investigator for safety, behavioural or administrative reasons. If a subject withdraws from the study, he/she may request destruction of any samples taken, and the investigator must document this in the site study records.

A reason for the withdrawal from the study must be captured in the eCRF.

A subject will also be withdrawn from the study, in consultation with the medical monitor and principal investigator, if any of the following stopping criteria are met:

- Laboratory parameters: Clinically important changes in laboratory parameters identified
- ECG: Clinically significant abnormality identified during the study that meet the QTc stopping criteria described in Section 5.5.4.
- Liver Chemistry: Meets any of the Liver chemistry stopping criteria (See Section 5.5.3 and [Appendix 5](#))
- Pregnancy: Positive pregnancy test (see [Appendix 3](#))

The following actions must be taken in relation to a subject who fails to attend the clinic for a required study visit:

[figure not shown]
- The site must attempt to contact the subject and re-schedule the missed visit as soon as possible.
- The site must counsel the subject on the importance of maintaining the assigned visit schedule and ascertain whether or not the subject wishes to and/or should continue in the study.
- In cases where the subject is deemed 'lost to follow up', the investigator or designee must make every effort to regain contact with the subject (where possible, 3 telephone calls and if necessary a certified letter to the subject's last known mailing address or local equivalent methods). These contact attempts should be documented in the subject's medical record.
- Should the subject continue to be unreachable, only then will he/she be considered to have withdrawn from the study with a primary reason of "Lost to Follow-up".

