### 5.5.4. QTc Stopping Criteria

- The *same* QT correction formula *must* be used for *each individual subject* to determine eligibility for and discontinuation from the study. This formula may not be changed or substituted once the subject has been enrolled.
- For example, if a subject is eligible for the protocol based on QTcB, then QTcB must be used for discontinuation of this individual subject as well.
- Once the QT correction formula has been chosen for a subject's eligibility, the *same formula* must continue to be used for that subject *for all QTc data being collected for data analysis*. Safety ECGs and other non-protocol specified ECGs are an exception.
- The QTc should be based on averaged QTc values of triplicate electrocardiograms obtained over a brief (e.g., 5-10 minutes) recording period. For example if a routine ECG demonstrates a prolonged QT, obtain 2 or more ECGs over a brief period and then use the averaged QTc values of the 3 ECGs to determine whether patient should be withdrawn from the study.

A subject who meets either of the bulleted criteria below will be withdrawn from the study:

- QTc > 500 msec OR Uncorrected QT > 600 msec
- [Change from screening (Visit 1) of QTc > 60 msec]

For patients with underlying **bundle branch block**, follow the discontinuation criteria listed below:

Screening (Visit 1) QTc with Bundle Branch Block	Discontinuation QTc with Bundle Branch Block
< 450 msec	> 500 msec
450 – 480 msec	≥ 530 msec

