**Any female subject who becomes pregnant while participating in the study will immediately discontinue study medication**

**12.4. Appendix 4: New York Heart Association Functional Classification of Congestive Heart Failure**

CLASS	PATIENT SYMPTOMS
I	Patients with cardiac disease but resulting in no limitation of physical activity. Ordinary physical activity does not cause undue fatigue, palpitation, dyspnea or anginal pain.
II	Patients with cardiac disease resulting in slight limitation of physical activity. They are comfortable at rest. Ordinary physical activity results in fatigue, palpitation, dyspnea or anginal pain
III	Patients with cardiac disease resulting in marked limitation of physical activity. They are comfortable at rest. Less than ordinary activity causes fatigue, palpitation, dyspnea or anginal pain
IV	Patients with cardiac disease resulting in inability to carry on any physical activity without discomfort. Symptoms of heart failure or the anginal syndrome may be present even at rest. If any physical activity is undertaken, discomfort increases

Adapted from [American Heart Association, 2011](#)]

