### Required Actions and Follow up Assessments following ANY Liver Stopping Event

Actions	Follow Up Assessments

 
• Immediately discontinue study treatment
 
• Report the event to GSK within 24 hours
 
• Complete the liver event CRF and complete an SAE data collection tool if the event also meets the criteria for an SAE
 
• Perform liver event follow up assessments
 
• Monitor the subject until liver chemistries resolve, stabilize, or return to within baseline (see MONITORING below)
 
	
 
• Viral hepatitis serology
 
• Only in those with underlying chronic hepatitis B at study entry (identified by positive hepatitis B surface antigen) quantitative hepatitis B DNA and hepatitis delta antibody.
 
• Blood sample for pharmacokinetic (PK) analysis, obtained within 4 weeks after last dose
 
• Serum creatine phosphokinase (CPK)
 

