
 
Do not restart/rechallenge subject with study treatment. Permanently discontinue study treatment and may continue subject in the study for any protocol specified follow up assessments
 
 
MONITORING:
 
For bilirubin or INR criteria:
 
 
Repeat liver chemistries (include ALT, AST, alkaline phosphatase, bilirubin) and perform liver event follow up assessments within 24 hrs
 
Monitor subjects twice weekly until liver chemistries resolve, stabilize or return to within baseline
 
A specialist or hepatology consultation is recommended
 
 
For All other criteria:
 
 
Repeat liver chemistries (include ALT, AST, alkaline phosphatase, bilirubin) and perform liver event follow up assessments within 24-72 hrs
 
Monitor subjects weekly until liver chemistries resolve, stabilize or return to within baseline
 
	
 
and lactate dehydrogenase (LDH).
 
Fractionate bilirubin, if total bilirubin <math>\geq 2 \times \text{ULN}</math>
 
Obtain complete blood count with differential to assess eosinophilia
 
Record the appearance or worsening of clinical symptoms of liver injury, or hypersensitivity, on the AE report form
 
Record use of concomitant medications on the concomitant medications report form including acetaminophen, herbal remedies, other over the counter medications.
 
Record alcohol use on the liver event alcohol intake case report form
 
 
For bilirubin or INR criteria:
 
 
Anti-nuclear antibody, anti-smooth muscle antibody, Type 1 anti-liver kidney microsomal antibodies, and quantitative total immunoglobulin G (IgG or gamma globulins).
 
Serum acetaminophen adduct high performance liquid chromatography (HPLC) assay (quantifies potential acetaminophen contribution to liver injury in subjects with definite or likely acetaminophen use in the preceding week [James, 2009]). NOTE: not required in China
 
Liver imaging (ultrasound, magnetic resonance, or computerised tomography) and /or liver biopsy to evaluate liver disease: complete Liver Imaging and/or Liver Biopsy CRF forms.
 

---	--

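### Section 5.5.2 withdraws a subject with a liver stopping event from the study; Appendix 5, which it cites, and Section 5.5.1 require only that study treatment stop

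*Protocol*

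**What the plan says.** Protocol Section 5.5.2 opens its list of stopping criteria with: "A subject will also be withdrawn from the study, in consultation with the medical monitor and principal investigator, if any of the following stopping criteria". One item reads "Liver Chemistry: Meets any of the Liver chemistry stopping criteria" and refers the reader to Section 5.5.3 and Appendix 5. Section 5.5.3 adds no rule on study participation. It points to Appendix 5 and, in 5.5.3.1, bars restarting treatment.

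The Appendix 5 table of required actions covers any liver stopping event, so its trigger is the same. Its first action is "Immediately discontinue study treatment". A later action is "Permanently discontinue study treatment and may continue subject in the study for any protocol specified follow up assessments".

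Section 5.5.1, on withdrawal from treatment, includes an abnormal liver function test among its reasons. It then says: "Subjects who have permanently withdrawn mepolizumab study treatment are not required to withdraw from the study". It asks sites to make every effort to complete the remaining visits unless there is a safety concern.

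Protocol Section 9.4.1 and SAP Section 7.1.2 both include in the primary analysis all data up to Week 32, including data from subjects who have stopped treatment.

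**The concern.** Section 5.5.2 requires the subject to leave the study. The appendix it cites for that same event stops treatment for good and lets the subject stay. No text gives one rule precedence over the other. A site that uses the permission in Appendix 5 departs from Section 5.5.2 and could be recorded as a protocol deviator for doing so.

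What is at stake is data. A subject who only stops treatment can still contribute ACQ-5 scores through Week 32, which the primary analysis is built to use. A subject withdrawn from the study contributes nothing after the Early Withdrawal Visit.

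**Working it through.** **The texts side by side**

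| Place | Trigger | Study treatment | Study participation |
|---|---|---|---|
| Protocol 5.5.2 | Any liver stopping criterion | Not stated separately | Must end, after consultation |
| Protocol Appendix 5 | Any liver stopping event | Stops permanently | May continue for protocol-specified follow-up |
| Protocol 5.5.1 | Treatment withdrawal; abnormal liver function test is a listed reason | Stops | Need not end; remaining visits encouraged |

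The QTc item in the same 5.5.2 list is a useful contrast. The section it cites, 5.5.4, agrees with it: "A subject who meets either of the bulleted criteria below will be withdrawn from the study". The liver item is the one whose cited text expressly allows the subject to stay.

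Both conflicting texts are current. Amendment 1 changed only the appendix number cited for the liver criteria, from 2 to 5.

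**ACQ-5 assessments lost if Section 5.5.2 is followed**

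Inputs: eight doses, at Weeks 0 to 28, and eight post-baseline ACQ-5 assessments, at Visits 3 to 10 (Protocol 7.1); an exit assessment about four weeks after the last dose, also for subjects who withdraw early (Protocol 4.1).

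After k doses, k - 1 post-baseline assessments have been made and the Early Withdrawal Visit adds one. The loss is 8 - (k - 1) - 1 = 8 - k.

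Scheduled post-baseline chemistry is at Weeks 4, 8, 12 and 24 and at Exit. Assuming the dose due on the day of the sample is given, an event found at Week 4, 8, 12 or 24 follows dose 2, 3, 4 or 7. The loss is then 6, 5, 4 or 1 assessments, and in each case Week 32 is among them. An event found at Exit costs none. Unscheduled samples could give other values of k.

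**Power**

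Inputs from Protocol 9.2.1: SD 0.96, 120 treated, 15% withdrawal, placebo effect -0.55, true change -0.86, two-sided 5%.

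With n = 120 × 0.85 = 102, SE = 0.96/√102 = 0.0951. The critical value is -0.55 - 1.96 × 0.0951 = -0.736, and power = Φ(0.31/0.0951 - 1.96) = 90.3%. This reproduces the protocol's -0.74 and 90%.

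The documents give no rate of liver stopping events, so I assume one to three additional subjects without Week 32 data.

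- Those subjects dropped completely: n = 101, 100, 99 gives 90.1%, 89.8%, 89.5%.
- Earlier visits of all 120 retained by the repeated-measures model: variance = (0.96²/120) × [(1 - ρ²) × 120/m + ρ²], where m is the number with Week 32 data and ρ is an assumed correlation. Going from m = 102 to m = 99, power moves from 91.4% to 90.8% at ρ = 0.5, and from 92.3% to 91.9% at ρ = 0.7.

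**The case against.** The strongest reply is that the texts can largely be reconciled. The permission in Appendix 5 is optional, so a site that withdraws the subject breaches neither text. The follow-up it allows could be read narrowly, as liver follow-up plus the exit visit that early withdrawals are asked to attend anyway. Section 5.5.2 also calls for consultation. The first part stands: a withdrawing site is not at fault. The rest does not remove the conflict. Consultation adds a step but does not turn a required withdrawal into a choice, and even on the narrow reading Appendix 5 keeps the subject in the study, which Section 5.5.2 does not.

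It can also be said that the planned 15% withdrawal already covers liver cases, so counting them as extra losses overstates the effect. That is fair, and it makes the power figures above pessimistic.

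A reader might infer three stronger points that the documents do not support:

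- That two sites could handle the same event differently and both be following the protocol. A site that keeps the subject is not following Section 5.5.2. Divergence is also limited, because Appendix 5 requires each stopping event to be reported to the sponsor within 24 hours and Section 5.5.2 brings in the medical monitor.
- That pregnancy shows the same contradiction. Appendix 3 says "Any female subject who becomes pregnant while participating in the study will immediately discontinue study medication" and provides for follow-up of the pregnancy. Both are compatible with study withdrawal under Section 5.5.2. Appendix 3 is silent on study participation, and silence is not conflict.
- That liver safety follow-up could lapse. Appendix 5 says "Monitor the subject until liver chemistries resolve, stabilize, or return to within baseline" and does not make this depend on study status.

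**Conclusion.** The contradiction is real and in current text. Section 5.5.2 requires study withdrawal for an event where Appendix 5 requires only permanent treatment discontinuation, and Section 5.5.1 supports Appendix 5. The analysis sections also fit Appendix 5, since they plan to use data collected after treatment stops.

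The consequence is minor. It is the loss of later ACQ-5 scores, including Week 32, for the few subjects who might have a liver stopping event before the eighth dose. The change in power is less than one percentage point under every assumption tried. That size rests on the assumed one to three events, the assumed correlations and a normal approximation; the textual conflict rests on none of them. It is worth correcting because the correction is specific and nearly free.

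**What to change.** Make three edits in a protocol amendment:

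1. Delete the liver chemistry bullet from the study-withdrawal list in Section 5.5.2. Rewording it in place would not work, because it would still sit under a lead-in that requires withdrawal.
2. Add to Section 5.5.1: *Subjects meeting a liver chemistry stopping criterion permanently discontinue study treatment, undergo Appendix 5 follow-up, and may continue remaining study visits provided there are no safety concerns, in consultation with the medical monitor.*
3. Add to the laboratory-parameters bullet in Section 5.5.2: *other than liver chemistry (see Section 5.5.1 and Appendix 5)*. Otherwise a marked ALT rise could still force study withdrawal as a clinically important laboratory change.

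The edit to 5.5.1 also settles the narrow reading of Appendix 5 by stating that the remaining visits are included. The cost is a few lines of text. No visit or assessment is added to the schedule, and neither Appendix 5 nor the SAP needs to change.
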